13.2. Treatment Rationale

13.2.1. Ataluren Schedule and Dose Selection

Dosing based on body weight will continue to be employed. Such dosing is common in pediatrics and reduces variability in exposure by accommodating differences in patient size across the span of ages of the boys who will participate in the clinical study program.

The schedule of drug administration is derived directly from Phase 1 PK modeling and from Phase 2 exposure information. The intent of administering 2 smaller doses at 6-hour intervals during the day and a larger dose at a 12-hour interval overnight (eg, at 7:00 AM, 1:00 PM, and 7:00 PM) is to optimally sustain target plasma concentrations while minimizing total exposures. This administration plan capitalizes on the effect of food in maintaining ataluren plasma concentrations and on nocturnal increase in plasma exposures observed in the Phase 1 studies [Hirawat 2007]. This schedule is likely to fit well with daily patterns of living for patients, thus enhancing compliance. As confirmation of that premise, compliance with ataluren dosing in Phase 2a and Phase 2b testing has been excellent.

13.2.2. Duration of Therapy

Because ataluren therapy will be administered chronically if the compound receives regulatory authority approval, it is important to continue to collect long-term safety and efficacy data during the ataluren development program. This open-label study is expected to generate additional long-term safety and efficacy information at the planned dosed level. This information will supplement data obtained in patients with nmDBMD who received ataluren in a prior PTC clinical study.

13.2.3. Safety Monitoring

In response to the occurrence of mild transaminase elevations in healthy volunteers participating in Phase 1 studies, and adrenal and renal findings in individual toxicology species, a specific safety monitoring plan for the target organs that these types of abnormalities represent has been established in this study. In addition, thresholds for evaluation and intervention have been established for other types of adverse events or laboratory abnormalities observed in the study. The intent is to protect patients, obtain a thorough assessment of any clinically relevant adverse events or laboratory abnormalities, and to offer recommendations for interruption and dose modification of ataluren in response to potential safety signals. The nature of these risks and the measures to monitor for them are to be reflected in the informed consent form.

As noted in Section 6.3.1, patients must be monitored closely for adverse events or laboratory abnormalities during the course of the study, safety findings deserving particular attention include hepatic, adrenal, renal, and electrolyte abnormalities. Section 6.3.1 provides information on actions to be taken in the event that abnormalities are noted on specified monitoring studies. Thresholds are provided for interrupting ataluren immediately, for interrupting ataluren after confirmation of a value beyond the threshold, or for continuing ataluren while evaluating for potential drug-related toxicity.

13.2.3.1. Hepatic Abnormalities

13.2.3.1.1. Overview

While toxicology studies in mice, rats, and dogs did not indicate adverse changes in hepatic pathology or serum aminotransferase levels, ataluren administration during Phase 1 studies in healthy volunteers was associated with Grade 1, reversible transaminase elevations in ALT and AST [Hirawat 2007]. During Phase 2a testing, serum transaminase levels have tended to improve in both DMD and cystic fibrosis patients (perhaps indicating evidence of response to

treatment). Thus, while clinical risk appears low, specific follow-up of markers of liver injury in this study is warranted.

13.2.3.1.2. Hepatic Monitoring Plan

Muscle breakdown results in ALT and AST values that are commonly 10- to 20-fold > ULN (Grade 3-4) in patients with DBMD. Consequently, it is not practical to exclude patients with high serum AST or ALT concentrations from enrollment in this study, and monitoring for hepatotoxicity must rely primarily on following patients for increases in bilirubin or GGT. Consistent with well-established guidelines [Abboud 2007] applied in this disease setting, even modest (Grade 2) alteration in bilirubin or GGT values should prompt interruption of ataluren. While serum ALT or AST values cannot routinely serve as measures of hepatic injury in boys with DBMD, significant increases in ALT (>150 U/L) in conjunction with a stable or falling CK should prompt increased frequency of laboratory monitoring and possibly an evaluation for potential hepatotoxicity.

13.2.3.2. Adrenal Abnormalities

13.2.3.2.1. Overview

Adrenal findings were noted in dogs receiving ataluren for ≥20 weeks. Anatomic findings included decreased adrenal weights and lymphohistiocytic infiltration with adjacent foci of parenchymal degeneration in the adrenal cortex. The morphology was not consistent with an immune-mediated hypoadrenalism (Addison's disease) and the dogs were asymptomatic throughout the entire study duration. These findings did not reverse at the end of 4 and 8 weeks of recovery following 20 and 52 weeks of dosing. An increase in serum basal adrenocorticotropic hormone (ACTH) values was observed and ACTH stimulation testing indicated that all dogs showed responses with increases in serum cortisol levels. However, because the magnitude of the cortisol response was not as great in animals receiving the mid- and high-dose of ataluren (500 and 1000 mg/kg/day) in comparison to controls, a no observed adverse effect level (NOAEL) for adrenal cortical function at the lowest ataluren dose level (250 mg/kg/day) was established. Consistent with lack of involvement of the zona glomerulosa, serum aldosterone values were unaffected and no serum electrolyte changes were seen. Steady state exposure in dogs at 250 mg/kg/day is ~0.8-fold the exposure in patients administered ataluren at the morning, midday, and evening doses of 10, 10 and 20 mg/kg/day, respectively. No drug-related effects on the adrenal gland have been seen in mice dosed for 26 weeks or in rats dosed for 24 months.

It is possible that patients participating in the ataluren studies could experience events similar to those occurring in animals. Pending the acquisition of further clinical safety information, a program of adrenal monitoring for patients receiving ataluren is being instituted using well-established techniques.

13.2.3.2.2. Adrenal Monitoring Plan

Adrenal monitoring in boys with DBMD presents unique challenges given the prevalence of chronic corticosteroid use in this population. While assessments of adrenal function in boys who are not using corticosteroids is straightforward, regular administration of prednisone or deflazacort to boys with DBMD is expected to induce secondary adrenal atrophy and reductions

in circulating glucocorticoids that may obscure the biochemical detection of potential ataluren-mediated adrenal toxicity. While this situation might seem concerning, it should be realized that boys who are receiving supraphysiological doses of corticosteroids are protected against endogenous hypoproduction of cortisol due to any cause [Ten 2001, Kyriazopoulou 2007].

In this context, the proposed monitoring plan for adrenal toxicity relies upon repeated assessment of tandem plasma markers – ACTH and cortisol to assess functional changes in glucocorticoid production, and secondary assessments of renin and aldosterone to measure mineralocorticoid production. Such use of these markers builds on evolving paradigms for semi-annual or annual monitoring adrenal function in individuals at high risk of primary autoimmune adrenal failure [Barker 2005, Coco 2006] and the well-established physiology of the adrenal gland and associated endocrine organs [Oelkers 1996].

In the evaluation of glucocorticoid function, it is understood that progressive primary failure of the adrenal gland results in decreased cortisol production and diminished negative feedback on pituitary gland generation of ACTH. In humans with an intact hypothalamic-pituitary-adrenal (HPA) axis, the pituitary gland compensates by progressively increasing plasma ACTH to maintain plasma cortisol levels. Cortisol production is preserved until adrenal cortical reserves become so low that ACTH hyperstimulation is no longer sufficient and cortisol concentrations finally fall. Thus, an early harbinger of a failure of primary glucocorticoid production is the detection of an elevated plasma ACTH concentration with a normal or falling cortisol level [Ketchum 1984, Oelkers 1992, De Bellis 1993, Blevins 1994]. Similar negative feedback loops exist for the renin-angiotensin-aldosterone system. In this situation, primary loss of aldosterone production in the adrenal results in compensatory hyperproduction of renin by the kidney. Thus, the earliest sign of a failure of mineralocorticoid production is the detection of an elevated plasma renin concentration with a normal or falling plasma aldosterone level [Ketchum 1984, De Bellis 1993, Betterle 2002].

Based on the findings of ataluren-associated effects on the ACTH-cortisol axis in the dog, assessments of plasma ACTH and cortisol are clearly warranted, especially in patients who are not receiving exogenous corticosteroids. In patients who are taking corticosteroids, endogenous plasma ACTH and cortisol levels will generally be low and the diagnostic sensitivity will be blunted. However, abnormal elevations of ACTH in this circumstance would still be a specific indication of glucocorticoid insufficiency and so should be monitored during ataluren dosing [Ten 2001].

The dog toxicology data do not indicate an ataluren-related risk of compromised mineralocorticoid production. Additionally, clinical measures of renin and aldosterone are markedly affected by age and normal reference ranges are very narrow. In boys who are taking ACE inhibitors or ARBs as prophylaxis/treatment of CHF, plasma renin values may be elevated and plasma aldosterone levels may be low due to these drugs [Azizi 1997, Hansen 1999]. For such patients, plasma renin and aldosterone concentrations may not prove useful as adrenal monitoring tools. Given these limitations, reliance will primarily be placed on monitoring of ACTH and cortisol values; routine assessment of the renin-aldosterone axis will only be performed if evidence of compromised corticosteroid production is observed. To facilitate

assessment of the renin-aldosterone axis in patients with treatment-emergent evidence of adrenal dysfunction, baseline renin and aldosterone values will be obtained in all patients prior to initiating treatment with study drug.

Based on these considerations, elevations of plasma ACTH should prompt confirmation of the elevated value, reassessment of cortisol levels, further diagnostic evaluation (potentially including ACTH stimulation testing [Dorin 2003]), and possible interruption of ataluren dosing. If patients who are not already receiving corticosteroids develop ataluren-related adrenal insufficiency, physiological replacement therapy with corticosteroids and/or mineralocorticoids can be instituted according to well-established protocols [Oelkers 1992, Ten 2001, Kyriazopoulou 2007].

13.2.3.3. Renal Abnormalities

13.2.3.3.1. Overview

Renal findings were seen in mice receiving 1 or 2 doses through 26 weeks of doses of ataluren. A NOAEL for the renal toxicity findings in mice has not been identified; the lowest observed adverse effect level (LOAEL) = 75 mg/kg/day. Exposure in mice at 75 mg/kg/day is 0.3-fold the exposure in patients administered at luren at the morning, midday, and evening doses of 10, 10 and 20 mg/kg/day, respectively. The renal finding was seen primarily in the distal nephron and involved some degenerative changes (apoptosis) and proliferation of renal epithelium. Renal tubular dilatation and proteinaceous material within the tubules also were seen. The structural integrity of the nephron was maintained, as degenerative/necrotic changes of large numbers of cells were not seen. A few glomeruli in the upper cortex were shrunken but the overall lesion did not primarily involve the glomeruli. The finding was occasionally accompanied by individual increases in serum blood urea nitrogen (BUN) and/or creatinine, however, a dose relationship for these parameters was not observed. The kidney findings were partially to completely reversible as soon as 2 weeks after cessation of dosing. The renal toxicity was observed in mice only, and has not been seen in rats dosed for 24 months or in dogs dosed for 52 weeks despite achievement of exposures in rats and dogs that were comparable to or greater than those observed in mice. In Phase 1 studies in healthy volunteers and Phase 2 studies in patients with DMD and cystic fibrosis, renal laboratory abnormalities have been infrequent.

During the Phase 2b double-blind study of ataluren in nmDMD (PTC124-GD-007-DMD), small increases in mean serum creatinine, BUN, and cystatin C were observed. The values tended to stabilize early in the study and did not increase further with continued treatment.

Renal abnormalities were observed in an international, multicenter, double-blind, placebo-controlled Phase 3 trial evaluating ataluren in patients ≥6 years of age with nonsense mutation cystic fibrosis in patients receiving concomitant ataluren and IV aminoglycosides (as described in the Ataluren Investigator Brochure). In patients who require treatment for serious infections, investigators should substitute other antibiotics for systemic aminoglycosides when clinically appropriate. If IV aminoglycosides are administered, study drug must be interrupted during the course of these antibiotics.

Study drug interruption should be considered with concomitant use of other potentially nephrotoxic antibiotics (eg, vancomycin). Caution should be exercised during concomitant use of other potentially nephrotoxic agents.

Patients requiring IV aminoglycoside or vancomycin therapy should be closely monitored in an appropriate setting. In patients receiving potentially nephrotoxic antibiotics such as IV aminoglycosides or vancomycin, antibiotic drug levels and serum creatinine and BUN should be followed closely. The antibiotic trough level and creatinine and BUN should be measured within 24 to 48 hours of administration of the first antibiotic dose, and further antibiotic dosing should be based on these results. Trough levels should be measured at intervals during the course of antibiotic treatment. Creatinine and BUN should be measured prior to initiating IV aminoglycoside or vancomycin therapy and at least twice a week during the course of antibiotic treatment.

Overall, the renal monitoring program included in this protocol considers nonclinical and clinical findings with ataluren, past experience with known nephrotoxicants, manifestations of DBMD, and current knowledge regarding exploratory renal toxicity biomarkers. A focus is placed on well-established clinical indictors of renal dysfunction for making diagnostic decisions and prompting treatment interruptions/ modifications in individual patients. The rationale for each of the decision-making parameters is discussed below.

13.2.3.3.2. Renal Monitoring Plan

Serum Cystatin C: GFR is a requisite component of renal testing to evaluate glomerular and nephron integrity. While "gold standard" methods of determining GFR (eg, infusions of inulin, iohexol, iothalamate, or technetium 99m-diethylenetriamine pentaacetic acid [99m-Tc-DTPA] with timed blood and urine assessments) can be employed, these methods are cumbersome and are often reserved for renal physiology laboratories at specialized centers [Guignard 2004, Stevens 2007]. In clinical practice, assessments of GFR have more typically relied upon determination of creatinine clearance during 24-hour urine collections or calculation based on nomograms using only serum creatinine. It is generally acknowledged that 24-hour urine collection in children is inaccurate and impractical due to compliance issues [Guignard 2004]. Calculation of GFR using only measurement of serum creatinine has long been standardized for children [Schwartz 1987]. However, because it is both filtered and secreted by the kidney, serum creatinine is acknowledged to be relatively imprecise and insensitive marker of renal damage [Herget-Rosenthal 2007, Schwartz 2007]. Moreover, serum creatinine is subject to variation based on endogenous and exogenous factors. This problem is particularly concerning in boys with DMD because the majority of creatinine in serum is derived from muscle [Wang 1996] and boys with DMD have decreased serum creatinine concentrations due to reduced muscle mass. A review of baseline serum creatinine values among the 38 boys with DMD participating in the ataluren Phase 2a study indicates low serum creatinine values (median 0.3, range 0.1-0.5 mg/dL). Additional sources of variability for boys with DMD may include ingestion of creatine (a substrate for creatinine production) [Escolar 2005] and treatment-mediated alterations in muscle fragility [Mendell 1989].

As an alternative to assessing GFR based on serum creatinine, serum cystatin C offers substantial advantages in the context of this protocol. Cystatin C is a low-molecular-weight [~13 kDa] proteinase inhibitor derived from all cells that is filtered by the glomerulus and degraded in the renal tubules [Herget-Rosenthal 2007]. The serum cystatin C concentration is almost solely dependent upon GFR and appears relatively unaffected by muscle mass or other conditions. An additional advantage is that circulating cystatin C changes more rapidly in response to multiple types of renal injury than creatinine [Herget-Rosenthal 2007]. Methods for measuring cystatin C are standardized and the correlations between serum cystatin C and GFR have been derived and confirmed in large studies involving healthy children and adults and those with renal dysfunction [Dharnidharka 2002, Grubb 2005, Zappitelli 2007]. Based on these considerations, values of serum cystatin above 1.33 mg/L should prompt diagnostic evaluation and interruption/modification of ataluren if required per protocol.

- Serum Creatinine: Given the widespread clinical familiarity with serum creatinine as a marker of renal dysfunction and as a monitoring tool for nephrotoxins in clinical practice [Gilead 2002, Gilead 2006, Novartis 2005], characterization of serum creatinine provides an appropriate frame of reference relative to other experiences. Because most participating boys with DMD are expected to have low normal values of serum creatinine due to reduced muscle mass, any values higher than the normal range may be cause for concern. Caveats regarding interpretation of serum creatinine in boys with DMD (particularly if there are food- or treatment-induced changes in serum creatinine values) dictate that an increase in serum creatinine above the age-specific normal range should prompt reevaluation of other safety parameters and potential interruption/modification of ataluren dosing.
- Serum Blood Urea Nitrogen: Considering its role in maintaining urine-concentrating ability, urea has major importance in renal physiology and its clinical measurement as a marker of renal dysfunction is long established. In the context of nephrotoxicity, elevations in BUN suggest disruption of tubular integrity [Vonderscher 2007]. In the nonclinical mouse studies of ataluren in which nephrosis was observed, BUN was elevated in some of the affected animals, confirming that this marker should also be measured in clinical studies of ataluren. Monitoring serum BUN, like monitoring creatinine, provides an additional frame of reference relative to other markers assessed within this study and in other studies of known nephrotoxicants. However, an elevation in BUN is not a specific signal of renal tubular injury, but also may reflect compromised renal tubular blood flow due to depressed cardiac output, medications, or dehydration [Guignard 2004, Stevens 2007]. For these reasons, a BUN increase ≥1.5 x ULN should prompt a review of potential pre-renal, renal, and post-renal causes for the abnormality as well as consideration of potential interruption/modification of ataluren dosing.
- Urine Protein:Creatinine and Urine Protein:Osmolality Ratio: Proteinuria can be an early marker for renal injury in experimental models [Amin 2004] and is commonly observed with even modest clinical decreases in renal function [National Kidney Foundation 2002]. Glomerular disease (eg, diabetic nephropathy) is often associated with albuminuria due to defects in exclusion of plasma proteins in the glomerular filtrate. Tubular injury (eg, as

observed in mice receiving ataluren) more often leads to increases in low-molecular-weight proteins (eg, beta-2 microglobulin, β 2-microglobulin, α 1-microglobulin retinol-binding protein, lysozyme) as tubular protein catabolism is compromised or proteins of injury are produced [Guignard 2004, Stevens 2007]. Because mice that developed nephrosis while receiving ataluren had proteinaceous material in the renal tubules on histological examination, monitoring of urine protein in humans receiving ataluren is additionally warranted.

Dipstick methods of protein screening are only semiquantitative, are relatively insensitive, and are confounded by exogenous substances and subjective interpretation [Kim 2007]. The presence of urinary protein may be masked in dilute urine or exaggerated in concentrated urine. For these reasons, a quantitative method of accessing proteinuria is planned in this study. Two methods will be assessed: urinary protein concentration relative to urinary creatinine concentration [Ginsberg 1983, Schwab 1987], and urinary protein concentration relative to urine osmolality [Wilson 1993, Morgenstern 2003]. These methods of screening, using spot urine samples, have been found to be as accurate as and more practical than quantification of urine protein during a 24-hour collection. Values for protein:creatinine of ≥0.2 mg/dL:mg/dL and of protein:osmolality of ≥0.15 mg/L:mOsm/kg have been established as abnormal [Morgenstern 2003]. While measurement of protein:creatinine is generally the preferred method in children [Morgenstern 2003], it is possible that low urinary creatinine excretion in boys with DMD may falsely elevate protein:creatinine ratios. For this reason, confirmed evidence that both measures are abnormal should stimulate further evaluation and intervention. Follow-up methods such as urine electrophoresis may be useful in discriminating among the types of proteins present and may suggest a site of injury (eg, an albumin-specific pattern with glomerular damage versus a diffuse multiple low-molecular-weight protein pattern with tubular damage) [Stevens 2007]. Confirmed proteinuria should prompt consideration of interruption/modification of ataluren dosing.

- Urine Blood: Blood in the urine may indicate pathology of the renal parenchyma or of the urinary collecting system (eg, ureters, bladder, and urethra). Like proteinuria, hematuria is commonly found in patients with minimal changes in GFR due to renal (particularly glomerular) dysfunction [National Kidney Foundation 2002]. Confirmed, persistent evidence of urinary blood by dipstick and/or microscopic examination will prompt further evaluation. Ultrasound or other imaging can evaluate for a potential renal cause for bleeding. Urology consultation can be obtained to assess for post-renal sources of hematuria. Clotting function and use of drugs that may impair platelet function will be reviewed. Confirmed, persistent hematuria in the absence of a post-renal source of bleeding or a bleeding diathesis will prompt potential interruption/modification of ataluren dosing.
- Serum Electrolytes: Assessments of serum electrolytes (sodium, chloride, potassium, bicarbonate, magnesium, calcium, and phosphorus) provide information regarding renal function that may supplement more primary assessments. Derangements in serum concentrations may reflect altered tubular handling of these ions. With worsening renal function, hyperphosphatemia and hypocalcemia may develop and reductions in serum bicarbonate or elevations in potassium may suggest an impaired ability of proximal tubules or collecting ducts to maintain acid-base balance [National Kidney Foundation 2002].

Given the cardiovascular and neurological consequences of severe derangements of serum potassium, calcium, or magnesium, evaluation of these ions is important to avoid potential secondary complications. Because transient Grade 1 alterations in the concentrations of electrolytes are very unlikely to be associated with significant secondary side effects, alterations to ≥Grade 2 are considered appropriate to prompt potential interruption/modification of ataluren dosing.

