Table 3 below provides information on actions to be taken in the event that abnormalities are noted in specified laboratory parameters. Thresholds are provided for interrupting ataluren immediately, for interrupting ataluren after confirmation of a value beyond the threshold, or for continuing ataluren while evaluating for potential drug-related toxicity. For adverse events or laboratory abnormalities not listed in Table 3 below, the investigator should use his/her judgment in determining whether the event or abnormality is clinically significant, whether diagnostic evaluation is warranted, and whether potential interruption of ataluren therapy is appropriate.

Table 3. Safety Monitoring Parameters and Actions To Be Taken

Organ System and Laboratory Parameter	Stop Study Drug Immediately, Confirm Abnormal Value, and Then Start Work-Up	Stop Study Drug After Confirming ^a Abnormal Value, and Then Start Work-Up	Continue Study Drug, Confirm Abnormal Value, and then Start Work-Up ^a
Hepatic			
Serum total bilirubin	≥Grade 3 (≥3.0 x ULN)	Grade 2 (1.5 – 3.0 x ULN)	
Serum GGT	≥Grade 3 (≥5.0 x ULN)	Grade 2 (>2.5 – 5.0 x ULN)	
Serum ALT			↑ of > 150 U/L with stable or ↓ CK
Adrenal			
Plasma ACTH		>ULN (and plasma cortisol <lln)< td="">>ULN (and cortisol WNL)	</lln)<>	>ULN (and cortisol WNL)
Renal			
Serum cystatin C	>2.00 mg/L	>1.33 – 2.00 mg/L	
Serum creatinine	≥ Grade 2 (≥1.5 x ULN for age)	Grade 1 (>ULN – 1.5 x ULN for age)	
Serum BUN	≥3.0 x ULN	≥1.5 – 3.0 x ULN	
Urine protein: urine creatinine (spot)		>0.40 mg:mg	
Urine protein: urine osmolality (spot)		>0.30 mg/L:mOsm/kg	
Urine blood (by dipstick)	4+ (Large)	3+ (Moderate)	2+ (Small)
Serum electrolytes	Grade 3-4	Grade 2	Grade 1
Serum Na+, high	>155 mmol/L	>150 – 155 mmol/L	
Serum Na+, low	<130 mmol/L		
Serum K+, high	>6.0 mmol/L	>5.5 – 6.0 mmol/L	
Serum K+, low	<3.0 mmol/L		
Serum Mg ²⁺ , high	>1.23 mmol/L		
Serum Mg ²⁺ , low	<0.4 mmol/L	<0.5 – 0.4 mmol/L	
Total serum Ca ²⁺ , high	>3.1 mmol/L	>2.9 – 3.1 mmol/L	
Total serum Ca ²⁺ , low	<1.75 mmol/L	<2.0 – 1.75 mmol/L	
Serum phosphorous	<0.6 mmol/L	<0.8 – 0.6 mmol/L	
Serum HCO ₃ -	<11 mmol/L	<16 – 11 mmol/L	

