5.7.2 Laboratory Tests

Hematological, serum biochemistry, adrenal laboratories, and urine data and their changes (only for continuous laboratory parameters) from baseline will be summarized by visit.

Shift tables for hematology and biochemistry data will also be presented showing change in CTCAE severity grade from baseline to each visit. For parameters for which a CTCAE scale does not exist, shift tables will be presented showing change in results from baseline (normal, low and high [or abnormal]) to each visit (normal, low and high [or abnormal]).

Summary of abnormalities in laboratory variables pre-defined for safety monitoring will be done per the following Table 2.

Table 2: Safety Monitoring Parameters and Actions to be Taken

Organ System and Laboratory Parameter	Stop Study Drug Immediately, Confirm Abnormal Value, and Then Start Work-Up	Stop Study Drug After Confirming ^a Abnormal Value, and Then Start Work-Up	Continue Study Drug, Confirm Abnormal Value, and then Start Work-Up ^a
Hepatic			
Serum total bilirubin	\geq Grade 3 ($\geq 3.0 \times$ ULN)	Grade 2 (1.5 – 3.0 x ULN)	---
Serum GGT	\geq Grade 3 ($\geq 5.0 \times$ ULN)	Grade 2 ($>2.5 - 5.0 \times$ ULN)	---
Serum ALT			\uparrow of >150 U/L with stable or \downarrow CK
Adrenal			
Plasma ACTH	---	$>$ ULN (and plasma cortisol $<$ LLN)	$>$ ULN (and cortisol WNL)
Renal			
Serum cystatin C	>2.00 mg/L	$>1.33 - 2.00$ mg/L	---
Serum creatinine	\geq Grade 2 ($\geq 1.5 \times$ ULN for age)	Grade 1 ($>$ ULN – $1.5 \times$ ULN for age)	---
Serum BUN	$\geq 3.0 \times$ ULN	$\geq 1.5 - 3.0 \times$ ULN	---
Urine protein: urine creatinine (spot)	---	>0.40 mg:mg	---
Urine protein: urine osmolality (spot)	---	>0.30 mg/L:mOsm/kg	---
Urine blood (by dipstick)	4+ (Large)	3+ (Moderate)	2+ (Small)

Organ System and Laboratory Parameter	Stop Study Drug Immediately, Confirm Abnormal Value, and Then Start Work-Up	Stop Study Drug After Confirming ^a Abnormal Value, and Then Start Work-Up	Continue Study Drug, Confirm Abnormal Value, and then Start Work-Up ^a
Serum electrolytes	Grade 3-4	Grade 2	Grade 1
Serum Na ⁺ , high	>155 mmol/L	>150 – 155 mmol/L	---
Serum Na ⁺ , low	<130 mmol/L	---	---
Serum K ⁺ , high	>6.0 mmol/L	>5.5 – 6.0 mmol/L	---
Serum K ⁺ , low	<3.0 mmol/L	---	---
Serum Mg ²⁺ , high	>1.23 mmol/L	---	---
Serum Mg ²⁺ , low	<0.4 mmol/L	<0.5 – 0.4 mmol/L	---
Total serum Ca ²⁺ , high	>3.1 mmol/L	>2.9 – 3.1 mmol/L	---
Total serum Ca ²⁺ , low	<1.75 mmol/L	<2.0 – 1.75 mmol/L	---

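### The protocol names high phosphorus as a sign of worsening renal function, but the pre-defined safety-monitoring summary has only low phosphorus limits and so cannot count it

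*Protocol*

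**What the plan says.** The rationale is in Protocol 13.2.3.3.2, under serum electrolytes. It opens without naming a direction: "Derangements in serum concentrations may reflect altered tubular handling of these ions". It then becomes specific: "With worsening renal function, hyperphosphatemia and hypocalcemia may develop", with lower bicarbonate or higher potassium as further possible signs of impaired renal handling. The action level, again without a direction, is that "alterations to ≥Grade 2 are considered appropriate to prompt potential interruption/modification of ataluren dosing".

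The limits are in Protocol 6.3.1, Table 3. Sodium, potassium, magnesium and calcium each have one row for high and one for low values. The row "Serum phosphorous" stands alone and holds two low-side entries, <0.6 mmol/L and "<0.8 – 0.6 mmol/L". SAP Table 2 carries the same row.

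SAP 5.7.2 gives that table its analysis role: "Summary of abnormalities in laboratory variables pre-defined for safety monitoring will be done per the following Table 2". For shift tables the main rule is: "Shift tables for hematology and biochemistry data will also be presented showing change in CTCAE severity grade from baseline to each visit". The fallback, with categories normal, low and high, is: "For parameters for which a CTCAE scale does not exist, shift tables will be presented showing change in results from baseline".

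**The concern.** Laboratory abnormalities, described by type and frequency among other features, are part of the primary endpoint (Protocol 3.3, SAP 3.3). The kidney is one of the target organs with its own monitoring plan. Protocol 13.2.3.3.1 reports that no no-effect level was found for the renal finding in mice, that the lowest effect level lies at 0.3-fold the patient exposure, and that mean creatinine, BUN and cystatin C rose slightly in Study 007.

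Against that background, one would expect the summary of pre-defined abnormalities to cover each electrolyte change that the protocol itself ties to failing renal function. For phosphorus it covers the opposite direction. At stake is a gap in one categorical safety table, and possibly in a second, for an analyte that is already measured at every laboratory visit.

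**Working it through.** The plan states no figure for this point, so the check compares passages and then goes through the planned outputs.

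**Step 1. Direction named against direction tabulated.**

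| Signal in Protocol 13.2.3.3.2 | Limit in that direction in Table 3 and SAP Table 2 |
|---|---|
| Low calcium | Yes (<2.0 – 1.75 and <1.75 mmol/L) |
| Low bicarbonate | Yes (<16 – 11 and <11 mmol/L) |
| High potassium | Yes (>5.5 – 6.0 and >6.0 mmol/L) |
| High phosphorus | No; only <0.8 – 0.6 and <0.6 mmol/L |

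Three of four match and one does not.

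**Step 2. Which planned outputs could show a high phosphorus value?**

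1. *Summary per SAP Table 2.* Not counted, because no row or column holds a high value. The separate renal-monitoring tables and listings in Protocol 10.4.5.2 are based on the conditions in section 6.3 and inherit the gap.
2. *Shift table.* Undetermined. The documents cite CTCAE Version 3.0 but do not reproduce its phosphorus scale. If that scale grades high values, they are counted. If it grades low values only, the result depends on how the fallback is read. Read by parameter, phosphorus has a scale, the fallback does not apply, and a high value gets no category of its own. Read by direction, the fallback applies and the value is shown as high. The SAP does not choose.
3. *By-visit summary.* Included. SAP 5.1 requires mean, median, minimum and maximum, so a high value affects the maximum. It gives no number of subjects. Under SAP 6.1 the last valid result in a window is the one analysed, so a high value followed by a normal repeat in the same window would not appear.
4. *Adverse events.* Counted if reported. Protocol 8.1.1 makes a laboratory abnormality reportable when it needs intervention or investigation beyond a repeat test. SAP 5.7.1 counts subjects with laboratory abnormalities reported as treatment-emergent events. Table 3 prompts no work-up for high phosphorus, so this route depends on the investigator's judgment.
5. *By-patient listings.* Shown, but not summarized.

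**Step 3. Data available.** Protocol Table 5 lists 23 biochemistry tubes per boy. The visit schedule gives the same figure: Screening (1) + Week 1 (1) + Weeks 12 to 240 every 12 weeks (240/12 = 20) + post-treatment (1) = 23. Results after the start of dosing: 23 − 2 = 21. With 96 boys all completing the Version 5.0 schedule, 96 × 21 = 2,016 results. This is the amount of data to which a high category could be applied at no extra collection cost. It is not a number of missed abnormalities.

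**The case against.** A reader might infer that high phosphorus is never counted, or that only a by-visit mean remains. The documents do not support that. Outputs 3 to 5 above all admit high values, and the adverse event tables are categorical counts of subjects.

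A reader might also infer from Table 3 that CTCAE grades low phosphorus only, since its electrolyte columns are labelled by grade. That is unsafe. Table 3 is a selective action table: low sodium, low potassium and high magnesium have no Grade 2 entry, so a missing limit there does not show a missing grade.

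Nor is phosphorus monitored only because it rises. The general sentence in 13.2.3.3.2 gives no direction, and low limits fit it. The section treats electrolytes as a supplement to more primary renal measures. Cystatin C, creatinine, BUN, two urine protein ratios and urine blood all have limits in both tables. No route is shown by which a boy with renal toxicity would go undetected.

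Finally, every column of Table 2 is a drug action, so adding a high-phosphorus row there would imply a clinical rule that the documents do not contain.

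All of this stands. It limits the point but does not remove it: the summary per Table 2 still omits a signal that the protocol names, and the shift-table rule is still silent on one-directional grading.

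**Conclusion.** The point holds in a limited form. One of the four electrolyte signals named in Protocol 13.2.3.3.2 has no limit in the named direction, so the summary of pre-defined abnormalities cannot count it. This follows from the documents alone and is certain. Whether the shift table also fails to count it cannot be settled without the CTCAE scale and a stated reading of the fallback rule; that part is an ambiguity, not a demonstrated omission.

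The number of boys affected cannot be estimated, because the documents give no rate of high phosphorus. The consequence is modest: a less complete laboratory part of the primary safety endpoint, for a supplementary renal marker that other outputs partly capture. It is worth correcting because the correction is cheap.

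**What to change.** **SAP 5.7.2.** State how a parameter with a CTCAE scale in one direction only is tabulated. Present phosphorus in a low/normal/high shift table against the central-laboratory reference range, alongside any shift by CTCAE grade. With the renal-monitoring summaries, report the number and percentage of subjects with any post-baseline phosphorus above that range. Take this count over all post-baseline results, not only the one kept per visit window. Label it as tabulation only and keep it outside the action columns of Table 2.

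**Protocol.** Reconcile the phosphorus row of Table 3 with section 13.2.3.3.2. Whether a high value should lead to any action is for the clinical team; no threshold or dosing rule is suggested.

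**Cost.** One extra shift table and one summary line, from results already in every biochemistry panel (Protocol 7.2.11). The downside is that some clinically minor high values will be counted.
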